2.5.2 Alternative to Study Participation

The alternative to study participation for all subjects is to continue to receive blood pressure care from their healthcare providers, which would include blood pressure checks, blood pressure lifestyle counseling/education, antihypertensive medication initiation and/or titration, and following their provider's treatment recommendations. This may also include referrals to specialty care (example: dieticians). Participants may choose to not participate in the study and at any time may discontinue their participation in the study.

Rationale for the necessity of exposing human participants to such risks: It is expected that this study will pose minimal risks to participants and the intervention outlined in this proposal (24-hour, clinic, home blood pressure monitoring, behavior change) are the same clinical interventions that can be prescribed during usual clinical care.

Why the value of the information to be gained outweighs the risks involved: Young adults with uncontrolled hypertension are at increased risks for premature heart failure, stroke, and chronic kidney disease. Therefore, the value of the information gained from this study far outweighs the risks involved.

2.5.3 Protection Against Risks

As indicated above, we expect minimum risk to participants. The primary pre-defined serious adverse events related to this study includes hypoglycemia among patients with diabetes mellitus starting a new exercise program. Subjects with any form of diabetes will be instructed to talk with their diabetes care team about adjusting their diabetes medication before starting a new exercise regimen and to discuss ways to treat hypoglycemia. Additionally, these recommendations will be reinforced with a handout from our study team about risk of hypoglycemia, signs, symptoms, and treatment of hypoglycemia and how to decrease their risk of hypoglycemia.

Patients with advanced chronic kidney disease (on dialysis or seeing a nephrologist) will be excluded to avoid serious adverse events with the Dietary Approaches to Stop Hypertension (DASH) diet, which may cause hyperkalemia. Once enrolled, study protocols will monitor and assess the presence of adverse events (AEs) and serious adverse events (SAEs) at all follow-up contacts.

Should a serious adverse event or adverse event be identified, it will be immediately reported as outlined later in this protocol. Should excessive risk to study participants be determined, the study will be stopped and all participants notified in a manner appropriate to the nature of the risk.

Emails will be used for sending 1) research clinic visit appointment reminders for all subjects (day, time, location, directions to UWHC or UWSMPH) and 2) handouts on blood pressure topics to reinforce the health coach phone call (intervention arm only - if this method was selected by the subject over postal mail). Each email will contain the minimum amount of information needed. Emails will be sent individually, with no cc or bcc. No group emails or lists will be used for this study. Emails will not contain sensitive protected health information (PHI). Per the University of Wisconsin HIPAA policy (www.hipaa.wisc.edu), the subject of the email will be "Documents for your UW Study".

Blood Pressure Cuffs: To minimize risks, patients will receive the appropriately sized cuff based on their upper arm circumference. In addition, the 24-hour ambulatory monitor will be started prior to leaving the research clinic to obtain at least two blood pressures to ensure comfort. Participants will also review information on how to contact the research staff in case additional questions, concerns, or new discomfort arise.

Muscle/joint discomfort: Participants will be instructed to consult their provider before starting a new exercise program.

Questionnaires/surveys: Participants will be informed that they can decline to answer any questions.

Health coach fidelity audio recordings:

- For Health Coach Calls Performed in Madison, WI: The audio digital recordings will be kept in a locked file cabinet in the PI's office located in the Health Innovation Program (HIP) at [name]. The audio files will be electronically transmitted by the MyHEART research staff to a UW Box file storage (approved by [name], UW SMPH; May 2017) accessible to [name] (lead researcher for this analysis) and a School of Nursing research student (a personnel change IRB application will be submitted once determined). The original and transmitted digital audio copies will be deleted/destroyed at the end of this study upon publication of the fidelity data.
- For Health Coach Calls Performed in Milwaukee, WI: The audio digital recordings will be kept in a locked file cabinet in an Aurora Health Care research office. Encrypted audio files will be emailed from a password protected research computer at Aurora Health Care to the study PI and study research coordinator, using Aurora Health Care and UW-Madison/Department of Medicine emails. The audio files will then be saved on the HIP network and maintained separately from other study documents in a password-protected database on password-protected media. The audio files will then be electronically transmitted by the MyHEART research staff to a UW Box file storage (approved by [name], UW SMPH; May 2017) accessible to [name] (lead researcher for this analysis) and a School of Nursing research student (a personnel change IRB application will be submitted once determined).

All original and transmitted digital audio copies will be deleted/destroyed at both research sites at the end of this study upon publication of the fidelity data.

Breach of Confidentiality - Identifying information: Subject confidentiality will be protected with the coded patient IDs whenever possible. Linking information will be maintained separately from other study documents in a password-protected database on password-protected media.

- Madison site: When handwritten or printed documents are required that include PHI or non-PHI with identifiers, the paper copies will be secured in a locked file cabinet within a locked office within the HIP Suite at [name] or within the UW Hospital and Clinics, Division of Cardiovascular Medicine (H4/5). Access to the paper records will be restricted to the PI and project personnel. As of May 2022, all paper records will be stored at the State of WI long term storage.
- Aurora site: When handwritten or printed documents are required that include PHI or non-PHI with identifiers, the paper copies will be secured in a locked file cabinet within a locked office within a Aurora Health Care research office, with oversight by the site PI. Access to the paper records will be restricted to the PI, site PI, and project personnel.

Analysis Data: Direct identifiers are removed by HIP and Aurora Programmers prior to data delivery to minimize the risk of loss of confidentiality. The data is labeled with a pseudo-identifier that is not derived from a patient identifying number. Analysis data is stored on a secure server under the control of the Health Innovation Program and access to study data is limited to persons who are approved to access it. Datasets for day-to-day analysis will be limited datasets (no direct identifiers; include zip codes and dates only; labeled with a pseudoidentifier). Details of data security protections are found in the "Privacy/confidentiality" section. Analysis data are never stored on paper. No sensitive information will be included in the analysis dataset. Encrypted Aurora Health Care data sets with coded patient IDs will be transferred to HIP and stored separately on the HIP network from data sets with linking information.

As of May 2022, all data will be transferred from HIP and stored on the UW Department of Obstetrics and Gynecology server. The transfer will proceed as follows:

HIP will copy and save files to a HIPAA compliant, FIPS140-2, encrypted disk. This disk has been approved by UW Cybersecurity as an acceptable media source to store PHI. In fact, if this disk were to be lost or stolen, only the business unit leadership would need to be notified (to replace the disk); UW Cybersecurity would not consider the loss a reportable event. The hard drive meets the security and compliance standards needed to store PHI. The hard drive will be stored in a locked cabinet in a locked office at HIP until MyHEART could bring it to Ob/Gyn.

No individual PHI will be released in presentation or publication. Only aggregate statistical output representing groups of subjects will be released or removed from the secure HIP or UW Ob/Gyn department servers.

The Wisconsin Network for Health Research (WiNHR) of UW-Madison's Clinical and Translational Science Award (CTSA) will oversee regulatory processes for this study, with the principal Investigator, site principal investigators, and the ICTR Data Monitoring Committee (DMC). The WiNHR staff have developed plans for assuring data accuracy and protocol compliance that will include biannual reviews with all research staff and WiNHR research coordinators. All study data will be documented and monitored in ICTR's REDCap. Such plans will include data verification and protocol compliance checks. The Principal Investigator will also be responsible for ensuring that the data for the project are securely stored, that storage is in compliance with University and federal regulations, and that no unauthorized persons have access (electronic or physical) to any participant-identifiable data. All HIPAA regulations and guidelines will be followed, and all study staff must complete approved human subjects and HIPAA training programs.

2.5.4 Adverse Event Reporting

MyHEART's data safety monitoring plan requires that investigators (PI, site-PIs) notify the NIH, DMC, and the University of Wisconsin IRB in a timely manner (consistent with IRB and NIH policies) of the occurrence of any SAE or any AE which is severe, unexpected, and possibly related to the protocol. This study does not involve pharmaceutical agents. Examples of SAE would be untoward medical or intervention occurrences that result in death, are life-threatening, require hospitalization or prolonging of existing hospitalization, or create persistent or significant disability/incapacity. Unanticipated AEs would include less serious problems that merit reporting because they are severe, unexpected, and possibly related to study participation. Any SAE will be queried and reported even if it appears that the serious adverse event is unrelated to intervention participation. The Principal Investigators will also be responsible for the accurate documentation, investigation, and follow-up of all study-related adverse events.

Adverse event assessment, recording, reporting, and investigation will be accomplished through staff training, structured/standardized assessments of untoward occurrences/events, and regular monitoring by site principal investigators using REDCap. The Principal Investigators have ultimate responsibility for ensuring that SAEs are detected and reported in a timely manner. Additionally, the IRB will receive an annual report of all SAEs and AEs meeting the criteria listed above.

Important medical events are those that may not be immediately life threatening, but are clearly of major clinical significance. They may jeopardize the subject, and may require intervention to prevent one of the other serious outcomes noted above. For example, treatment of bronchospasm in an emergency department would typically be considered serious. The primary pre-defined serious adverse events related to this study include hypoglycemia among patients with diabetes mellitus starting a new exercise program. All adverse events that do not meet any of the criteria for 'serious' should be regarded as *non-serious adverse events*. Throughout the study, any new clinically significant findings/abnormalities that meet the definition of an adverse event will also be recorded and documented as an adverse event.

Adverse Event Reporting Period: Adverse events must be reported once the subject undergoes any study procedures, and adverse events must be reported during the entire active study period and for 30 days following the last administration of study treatment.

Withdrawal of subjects: Any subject who experiences an adverse event or serious adverse event will be immediately withdrawn from the study. All subjects have the option to withdraw from the study at any time. Subjects will also be immediately withdrawn from the study if they report being pregnant, planning to become pregnant, or develop a medical condition (even if unrelated from this study) that prevents them from ongoing participation in the study.

Post-study Adverse Event: All unresolved adverse events will be followed by the investigator until the events are resolved, the subject is lost to follow-up, or the adverse event is otherwise explained. At the last scheduled visit, the investigator will instruct each subject to report any subsequent event(s) that the subject, or the subject's personal physician, believes might be related to participation in this study. The investigator should notify the study sponsor, DMC, and IRB of any serious adverse event or death occurring up to 30 days after the subject has discontinued or terminated study participation that may be related to this study.

Hospitalization, Prolonged Hospitalization, or Surgery: Any adverse event that results in hospitalization or prolonged hospitalization will be documented and reported as a serious adverse event unless specifically instructed otherwise in this protocol. Any condition responsible for surgery should be documented as an adverse event if the condition meets the criteria for an adverse event.

Neither the condition, hospitalization, prolonged hospitalization, nor surgery are reported as an adverse event in the following circumstance: Hospitalization or prolonged hospitalization for diagnostic or elective surgical procedures for a preexisting condition. Surgery should **not** be reported as an outcome of an adverse event if the purpose of the surgery was elective or diagnostic and the outcome was uneventful.

Referral for treatment, counseling, or other necessary follow-up. Participants who report excess alcohol use, psychiatric illness (new or chronic), and/or willingness to quit smoking will be referred to their primary care provider for necessary follow-up. Subjects will also receive written handouts about alcohol/tobacco cessation resources (e.g., Wisconsin Tobacco Quit Line). Charges for treatment, counseling, and/or follow-up will be the sole responsibility of the subject.

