4.7.2 When and How to Withdraw Subjects

Participants will be educated on the consent form that they are able to withdraw at any time without adverse effects to receiving healthcare services.

Women that are currently pregnant or plan to become pregnant during enrollment screening will be excluded from study participation. If a participant becomes pregnant during the study, she is excluded immediately from further participation in all study activities. The presence/absence of birth control is not an inclusion or exclusion criteria. Pregnancy testing is not part of the study protocol. Once enrolled in the study, individuals in either the usual care or intervention group who become ineligible during the study (e.g., self-report of a new condition in the list of exclusion criteria) will be informed that their participation has ended and will be provided the reason for ending their study participation.

No medications will be administered by the study staff. Procedures are not needed to transition subjects of study agents or alternate therapy if withdrawn from this study.

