8.1 Specifications of Safety Parameters

8.1.1 Definition of Adverse Events (AE)

An *adverse event* (AE) is any symptom, sign, illness, or experience that develops or worsens in severity during the course of the study. Intercurrent illnesses or injuries should be regarded as adverse events. Abnormal results of diagnostic procedures are considered to be adverse events if the abnormality:

- results in study withdrawal
- is associated with a serious adverse event
- is associated with clinical signs or symptoms
- leads to additional treatment or to further diagnostic tests
- is considered by the investigator to be of clinical significance

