8.2 Classification of an Adverse Event

8.2.1 Severity of Event

The following guidelines will be used to describe severity:

Mild – Events require minimal or no treatment and do not interfere with the participant’s daily activities.

Moderate – Events result in a low level of inconvenience or concern with the therapeutic measures. Moderate events may cause some interference with functioning.

Severe – Events interrupt a participant’s usual daily activity and may require systemic drug therapy or other treatment. Severe events are usually potentially life threatening or incapacitating.

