8.3 Time Period and Frequency for Event Assessment and Follow-Up

The occurrence of an AE or SAE may come to the attention of study personnel during study visits and interviews of a study participant presenting for medical care, or upon review by a study monitor. All AEs including local and systemic reactions not meeting the criteria for SAEs will be captured on the appropriate CRF. Information to be collected includes event description, time of onset, clinician’s assessment of severity, relationship to study product (assessed only by those with the training and authority to make a diagnosis), and time of resolution/stabilization of the event. All

AEs occurring while on study must be documented appropriately regardless of relationship. All AEs will be followed to adequate resolution.

Any medical condition that is present at the time that the participant is screened will be considered as baseline and not reported as an AE. However, if the study participant's condition deteriorates at any time during the study, it will be recorded as an AE. UPs will be recorded in the data collection system throughout the study.

Changes in the severity of an AE will be documented to allow an assessment of the duration of the event at each level of severity to be performed. AEs characterized as intermittent require documentation of onset and duration of each episode.

The PI will record all reportable events with start dates occurring any time after informed consent is obtained until 30 days (for non-serious AEs and SAEs) after the last day of study participation. At each study visit, the investigator will inquire about the occurrence of AE/SAEs since the last visit. Events will be followed for outcome information until resolution or stabilization. Breaches of confidentiality and emotional upset will be reported to the PI who will then review the incident with the study staff, information technology groups, and follow-up with the participant. The PI is responsible for making the reports to the DSBM, IRB and NHLBI.

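### Section 2.5.4 withdraws anyone with any adverse event, however mild or unrelated, and no section provides for blood pressure measurement afterwards

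*Combined protocol and SAP*

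**What the plan says.** **The rule.** Section 2.5.4 (Withdrawal of subjects) states: "Any subject who experiences an adverse event or serious adverse event will be immediately withdrawn from the study". It has no limit on severity, relatedness or arm. The same paragraph later withdraws participants who are or plan to become pregnant, and those who "develop a medical condition (even if unrelated from this study) that prevents them from ongoing participation in the study".

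**What counts as an AE.** Section 8.1.1 covers any new or worsening symptom, sign, illness or experience, and adds: "Intercurrent illnesses or injuries should be regarded as adverse events". Section 8.2.1 describes the mild grade as: "Events require minimal or no treatment".

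**Text pointing to a narrower intent.** Section 8.1.1 lists five alternative grounds for calling an abnormal diagnostic result an AE; one is that it "results in study withdrawal". Section 8.3 says "At each study visit, the investigator will inquire about the occurrence of AE/SAEs since the last visit" and "AEs characterized as intermittent require documentation of onset and duration of each episode".

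**Withdrawal and its handling.** Section 4.7.2 names participant choice, pregnancy and newly arising ineligibility; participants who become ineligible "will be informed that their participation has ended and will be provided the reason for ending their study participation". It does not mention AEs. Section 4.7.3 specifies intention-to-treat analysis, multiple imputation and sensitivity analyses for missing data, with no BP measurement after withdrawal.

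**The concern.** Taken literally, the sentence ends participation for trivial and unrelated events. Site staff must either follow it and lose outcome data, or ignore an explicit instruction and depart from the protocol. The two sites could choose differently.

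What is at stake is the 6-month co-primary systolic and diastolic BP (SBP, DBP). A participant with a sore knee or a respiratory infection can usually still have BP taken. Values missing for health reasons are harder to impute credibly than values missing at random, and a sensitivity analysis cannot restore a reading that was never made.

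Loss could also differ by arm. Section 2.5.3 assesses AEs at all follow-up contacts, only the intervention arm has 12 coach calls (section 5.4.2), and section 2.5.1 names muscle or joint discomfort after new exercise as a risk. More AE withdrawal in the intervention arm is therefore plausible.

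**Working it through.** **1. Reading the sections together**

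- 2.5.4 against itself: if every AE already means withdrawal, the later trigger for a condition that prevents participation is largely redundant.
- 2.5.4 against 8.1.1: withdrawal as one of five alternative grounds implies that some AEs do not lead to it.
- 2.5.4 against 8.3: repeated enquiry and episode-by-episode recording sit more naturally with participants who stay on study.
- 2.5.4 against 4.7.2: silence on AEs, not a contrary rule.

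These are tensions by implication. None overrides the sentence.

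**2. Reproducing the stated power (section 6.1)**

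Inputs: differences 6.3 and 4.0 mmHg, SDs 13.6 and 9.7, two-sided 0.025 each, effective N 264 (132 per arm). Noncentral-t power for two means gives 0.934 (SBP) and 0.863 (DBP); the normal approximation gives 0.936 and 0.866. The plan states 0.94 and 0.87, so it reproduces.

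**3. Loss already absorbed**

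1 − 264/340 = 22.4%. The stated 15% dropout alone would leave 340 × 0.85 = 289.

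**4. Equal AE withdrawal in both arms (rates assumed)**

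With r first AEs per person-year, the share with no AE by 6 months is s = exp(−0.5r). Per-arm n is 170s if AEs are the only loss, or 144.5s on top of 15% dropout.

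Rates at which N reaches 264:
- AEs the only loss: −ln(264/340)/0.5 = 0.51 per person-year.
- On top of 15%: −ln(264/289)/0.5 = 0.18 per person-year, or 1 − 264/289 = 8.7% of those otherwise retained.

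| r | share with an AE by 6 months | only loss: N, SBP/DBP power | on top of 15%: N, SBP/DBP power |
|---|---|---|---|
| 0.1 | 4.9% | 323, 0.97/0.93 | 275, 0.94/0.88 |
| 0.2 | 9.5% | 308, 0.96/0.91 | 261, 0.93/0.86 |
| 0.5 | 22.1% | 265, 0.93/0.86 | 225, 0.89/0.80 |
| 1.0 | 39.3% | 206, 0.86/0.76 | 175, 0.79/0.68 |

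**5. Unequal AE withdrawal on top of 15% (shares assumed)**

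- 10% intervention, 5% usual care: total loss 1 − 0.85 × 0.90 = 23.5% and 1 − 0.85 × 0.95 = 19.3%; n = 130.1 and 137.3 (N 267); power 0.94/0.87.
- 20% intervention, 5% usual care: total loss 1 − 0.85 × 0.80 = 32.0% and 19.3%; n = 115.6 and 137.3 (N 253); power 0.92/0.84.

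**6. Shift in the SBP difference before imputation**

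Within an arm, the retained mean differs from the full-arm mean by (share withdrawn) × (gap between withdrawn and retained). With an assumed 5 mmHg gap:

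- Same gap in both arms: (0.10 − 0.05) × 5 = 0.25 mmHg; (0.20 − 0.05) × 5 = 0.75 mmHg.
- Gap in the intervention arm only: 0.10 × 5 = 0.5 mmHg; 0.20 × 5 = 1.0 mmHg.

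Against the assumed 6.3 mmHg effect, the range is 0.25/6.3 = 4% to 1.0/6.3 = 16%.

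**The case against.** **The sentence is plainly not meant literally.** Section 2.5.4 opens by limiting prompt notification to serious AEs and to AEs that are severe, unexpected and possibly related. That supports a narrower intent, but it governs notification, and nothing carries the limit over to withdrawal.

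**There is no second rule to conflict with.** This largely stands. A reader might infer that 4.7.2, 8.1.1 and 8.3 state a rival rule; they do not. No section says a participant with an AE stays in. Section 4.7.2 only omits AEs, and its ineligibility route reaches the investigator-discretion item in the exclusion list, which could accommodate an AE withdrawal. The enquiry in 8.3 is also how a first AE is found, and recording episodes fits AE follow-up to resolution, which continues after withdrawal.

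**The sizing is assumed and often reassuring.** This stands. Power is at or near plan up to about 0.2 per person-year, and the 10% versus 5% case returns the stated power. The tables also assume that every AE by 6 months costs the outcome, whereas an AE first disclosed at Visit 3 need not cost the clinic BP taken that day. On the other side, no document shows that rates of 0.1 to 0.2 describe a rule that counts every mild symptom.

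**Unequal detection by arm is inferred.** This stands in part. A reader might conclude that coach calls will uncover more AEs. The description of the calls in 5.4.2 lists no AE enquiry, and 8.3 places enquiry at study visits; only the general phrase in 2.5.3 supports detection by call. Usual care also has contacts: a scheduler call before Visit 3 (5.4.3) and phone surveys in both arms (9.4).

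**Imputation and sensitivity analyses are planned.** They are, and they may recover part of the information. The full SAP, an appendix to the protocol, was not available for this review.

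**Conclusion.** The point holds and should be fixed. The certain part is textual: an unqualified instruction, a broad AE definition, no section that narrows it, and no provision for BP after withdrawal. Followed as written, it discards co-primary BP that could have been measured.

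The numerical effect is not established. Power drops materially only if AE withdrawals on top of 15% dropout go well beyond 8.7% of those otherwise retained, or well beyond 0.51 per person-year if they are the only loss. Possible unequal, health-related loss matters more than power; its direction is plausible and its size unknown. The 0.25 to 1.0 mmHg range rests on an assumed 5 mmHg gap and assumed withdrawal shares, before imputation. The documents do not support a claim that the trial is underpowered or biased by a known amount. Confidence is medium, because the AE rate is not given and the SAP appendix was not seen.

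**What to change.** 1. Replace the sentence in 2.5.4 with: *An AE or SAE leads to stopping the intervention (intervention arm) or study procedures only when the investigator judges continuation unsafe or the participant asks to stop. BP at the remaining visits is still attempted in both arms unless consent is withdrawn, measurement is unsafe, or another withdrawal rule applies (pregnancy, ineligibility under 4.7.2, non-return under 9.4).*
2. Add to 4.7.3: *BP measured after the intervention stops is used in the intention-to-treat analysis.*
3. Report the existing endpoint of withdrawal rate and reason (3.1.3) by arm, separating stopped intervention from stopped measurement.

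Leave the wording of 4.7.2 unchanged. It also covers usual-care participants, who have no coaching to stop, and people who newly meet any exclusion, such as prisoners, for whom visits should not simply continue.

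**Cost.** A protocol amendment with IRB review, an investigator judgement per AE, and visit costs for participants who would otherwise have left. Payments for Visits 3 to 6 are at most 30 + 20 + 30 + 20, plus the $20 card, or $120 each (section 4.6.6). If an assumed 10% of 340 (34 people) were affected, that is at most 34 × 120 = $4,080, within the $170 per participant already planned. The documents give no staff or device budget.
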